## **16.5. Implementation of Tipping Point Analysis for the Key Secondary Endpoints**

This section describes the tipping point analysis for the following key secondary endpoints: serum androstenedione, HOMA-IR, weight and percent total fat mass. The timepoint of interest for each endpoint is Week 24 with the exception of serum androstenedione where change from baseline to Week 4 is defined as the endpoint. Note that the guidance given in the text below for the tipping point analyses refers to Week 24; however, Week 4 will be used for analyses of serum androstenedione as defined in Section 9.4.1.

A tipping point sensitivity analysis will be performed to assess the robustness of the missing data assumptions for each of the key secondary endpoints listed above. The following steps will be taken to implement the tipping point analysis for each key secondary endpoint:

- 1) For the 100 imputed datasets created (as described in Section 16.2), if a subject was originally missing the Week 24 endpoint value, add *delta* (see rules below) to the imputed Week 24 endpoint value. Calculate the percent change or change from baseline (depending on the original endpoint) to Week 24 for all subjects as applicable for each key secondary endpoint:
  - If the Week 24 endpoint value is non-missing: percent change from baseline =  $(\text{Week 24 value} - \text{baseline value}) / \text{baseline value} \times 100$ ; and change from baseline =  $(\text{Week 24 value} - \text{baseline value})$ .
  - If the Week 24 endpoint value is missing and the subject is in either the crinecerfont treatment group or placebo treatment group: percent change from baseline =  $(\text{Week 24 delta-adjusted imputed value} - \text{baseline value}) / \text{baseline value} \times 100$  and change from baseline =  $(\text{Week 24 delta-adjusted imputed value} - \text{baseline value})$ .
- 2) Analyze the percent change from baseline (or change from baseline) to Week 24 for the values in each of the 100 imputed datasets using ANCOVA (as specified in 9.2.1) using PROC MIXED. Use PROC MIANALYZE to combine the results and obtain the LS mean statistics (within treatment, and treatment differences).
- 3) If the p-value in the previous step was not significant (i.e.,  $>0.05$ ), then no additional analyses are needed. If the p-value was significant, repeat the previous steps using the next values of *delta*. Continue to do this until significance is lost, or all combinations of *deltas* (defined for each treatment group) have been analyzed.

The following rules will be used for defining *delta*:

- The initial delta will be = 0 for each key secondary endpoint (ie, an analysis of the original, multiply imputed datasets)
- For subjects in the crinecerfont treatment group, the second delta will be defined based on the information in [Table 11](#) below for each key secondary endpoint. If this is significant, continue to increase delta based on [Table 11](#) until significance is lost.
- For subjects in the placebo treatment group, the second delta will be defined based on the information in [Table 11](#) below for each key secondary endpoint. If this is significant, continue to decrease delta based on [Table 11](#) until significance is lost.

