### 9.1. Multiple Comparisons and Multiplicity

The testing procedure described below will be used to control the familywise Type I error rate for the primary and key secondary endpoints (Figure 1). The promising zone method as planned in this study was shown to not inflate the type I error, as described in the simulation report attached to the Adaptation Plan. All significance levels noted below are 2-sided. All other p-values will not be adjusted for multiplicity and should be considered as nominal p-values.

- The primary endpoint will be tested using a significance level of 0.05.
- If the primary endpoint is statistically significant, then the first 2 key secondary endpoints will be tested using an unequal allocation of significance levels. The change from baseline at Week 4 in androstenedione will be tested using a significance level of 0.02. The achievement of a reduction in glucocorticoid daily dose to physiologic levels ( $\leq 11 \text{ mg/m}^2/\text{day}$  hydrocortisone equivalent adjusted for BSA) will be tested using a significance level of 0.03.
- The family of remaining key secondary endpoints will be tested using the Holm procedure (Holm, 1979). The significance level for this family of endpoints will be dependent on whether the first 2 key secondary endpoints are statistically significant (Wiens, 2003). If both are statistically significant, then the significance level for this family of endpoints will be 0.05. If only one is statistically significant, then the significance level for that endpoint will be used for this family of endpoints. If neither is significant, then this family of endpoints will not be tested for statistical significance. However, nominal p-values will be produced.

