### **9.3.3. Sensitivity Analyses of the Primary Efficacy Results**

The assumptions relative to the ANCOVA model (e.g. linearity, normality) specified for the primary analysis of the primary endpoint will be checked and any violations of these assumptions will be handled through non-parametric statistical methods.

A tipping point sensitivity analysis will be performed to assess the robustness of the missingness assumptions. This sensitivity analysis is based on “delta adjustments” which is a commonly used approach to assess the impact of missing data in clinical trials (O’Kelly and Ratitch, 2014). The imputed Week 24 glucocorticoid daily dose values (from the MI procedure described in Section 16.1) for subjects in either the crinecerfont treatment group or the placebo treatment group will be delta-adjusted (with a range of plausible penalties for each treatment group) until the treatment difference at Week 24 is no longer statistically significant. The implementation procedure for the tipping point analysis is described in Appendix 16.4. The combinations of delta adjustments that tip the result from statistically significant to insignificant along with the corresponding insignificant p-values will be presented in a table and may be presented in a figure.

A complete-case sensitivity analysis will also be performed to test the robustness of the multiple imputation procedure. The ANCOVA analysis for the primary endpoint will be repeated using only subjects with observed data at Week 24. Subjects who are missing the Week 24 primary endpoint will be excluded from the analysis.

Descriptive statistics and LS means for the sensitivity analyses will be presented by treatment group along with the LS-mean treatment difference, 95% confidence intervals, and nominal p-values.

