## **9.4. Analysis of Key Secondary Efficacy Endpoints**

### **9.4.1. Serum Androstenedione**

The first key secondary endpoint is the change from baseline in serum androstenedione at Week 4. The pre-morning glucocorticoid dose androstenedione values at baseline and Week 4 will be used in the calculation of this endpoint (as defined in Section 6.3.4). If a subject is missing their baseline or Week 4 pre-glucocorticoid dose androstenedione value, then the post-glucocorticoid androstenedione values at baseline and Week 4 will be used instead. The primary analysis of this endpoint will be performed using an ANCOVA model as described in Section 9.2.1. Subjects who are missing all androstenedione levels at Week 4 will have their Week 4 data imputed through the multiple imputation procedure described in Section 16.2.

Statistical significance for the treatment comparison will be determined using the multiple comparison procedure described in Section 9.1. Descriptive statistics and LS means will be presented by treatment group along with the LS mean treatment difference, 95% confidence intervals, and p-value.

Descriptive statistics will be presented by treatment group and visit for the serum androstenedione observed and change from baseline values through Week 24. For visits where androstenedione is collected more than once (e.g., Day 1), each visit will be presented with the pre- and post- morning GC dose androstenedione values. The androstenedione observed values from the two screening visits and the average of these values will also be summarized.

Mean ( $\pm$ SEM) values of serum androstenedione at each visit will be summarized in line graphs by treatment group. For visits where androstenedione is collected more than once, each visit will be presented with the pre- and post- morning GC dose androstenedione values on separate plots. Similar graphs will be presented for the changes from baseline.

A tipping point sensitivity analysis of change from baseline in serum androstenedione at Week 4 will be performed to assess the robustness of the missingness assumptions as was described for the primary endpoint in Section 9.3.3. The implementation procedure for the tipping point analysis is described in Appendix 16.5 for each key secondary efficacy endpoint.

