A complete-case sensitivity analysis will also be performed to test the robustness of the multiple imputation procedure. The ANCOVA analysis for change from baseline in serum androstenedione will be repeated using only subjects with observed data at Week 4. Subjects who are missing Week 4 androstenedione values will be excluded from the analysis.

As a supplementary analysis, the percent change from baseline in serum androstenedione will be analyzed using the same method as described in the primary analysis of this endpoint. Missing data will also be imputed using the same methods as described in the primary analysis of this endpoint.

As a supplementary analysis, the change from baseline to Week 4 in serum androstenedione will be analyzed using the average of the two screening post-GC dose visit values and the Day 1 post-GC dose value as compared to the Week 4 post-GC dose androstenedione value. If one or more of the screening or Day 1 values is missing or if collected pre-GC dose, then the average of the remaining values will be used instead. This analysis will be performed using an ANCOVA model as described above. Missing data will also be imputed using the same methods as described in the primary analysis of this endpoint.

As a supplementary analysis, the change from baseline to Week 4 in serum androstenedione, derived as a multiple of the ULN (calculated as observed value divided by the ULN value) [based on age and sex], will be analyzed using the same method as described in the primary analysis of this endpoint. Missing data will also be imputed using the same methods as described in the primary analysis of this endpoint.

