**Table 11: Delta-Adjustment Values**

Key Secondary Endpoint	Second Delta		If still significant after the second delta, increase or decrease delta by the following:	
	Crinecerfont	Placebo	Crinecerfont	Placebo
Serum Androstenedione (nmol/L)	0.1745	-0.1745	0.1745	-0.1745

HOMA-IR	0.1	-0.1	0.2	-0.2
Weight (kg)	1	-1	1	-1
%Total Fat Mass	1	-1	1	-1

Note that if the increment or decrement of delta is too large or too small, then the delta may be adjusted in order to make the number of comparisons reasonable. If significance is not lost or is lost slowly, some values of delta may be omitted from the final table. The tipping point will be defined as the combination of delta values that result in loss of significance.

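### The tipping-point searches for Week 4 androstenedione and the physiologic-dose responder stop at p > 0.05, although these endpoints are tested at 0.02 and 0.03

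*SAP*

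**What the plan says.** SAP Section 9.1 splits the 0.05 between the first two key secondary endpoints once the primary endpoint is significant. For the first, "The change from baseline at Week 4 in androstenedione will be tested using a significance level of 0.02". The physiologic-dose responder "will be tested using a significance level of 0.03". Both levels are two-sided, and no alpha passes from one endpoint to the other. Section 9.4.1 ties androstenedione to that scheme: "Statistical significance for the treatment comparison will be determined using the multiple comparison procedure described in Section 9.1".

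Sections 9.4.1 and 9.4.2 plan tipping-point analyses for these endpoints in the manner of Section 9.3.3, which states the output: "The combinations of delta adjustments that tip the result from statistically significant to insignificant along with the corresponding insignificant p-values will be presented". The steps are in Appendix 16.5 (androstenedione, HOMA-IR, weight, percent total fat mass) and Appendix 16.6 (responder). Step 3 of 16.5 reads "If the p-value in the previous step was not significant (i.e., $>0.05$ ), then no additional analyses are needed", and step 4 of 16.6 uses the same words. Both appendices close with the definition "The tipping point will be defined as the combination of delta values that result in loss of significance". The same stopping sentence also stands in 16.4 for the primary endpoint.

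**The concern.** A tipping-point analysis asks how unfavourable the missing values must be before the claim fails. That only makes sense if failure is judged at the level at which the claim was made. For the primary endpoint this is 0.05, so the rule in 16.4 is right. For androstenedione and the responder the claim is lost once p exceeds 0.02 or 0.03, but the search continues until p exceeds 0.05.

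The report can then show a wider margin against missing-data assumptions than the claim has, and never a narrower one. The search also runs for a claim that was never won: androstenedione with p = 0.04 at delta = 0 has failed under Section 9.1, yet 16.5 would go on to report a non-zero tipping delta.

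**Working it through.** **Inputs from the documents.** Levels of 0.02 and 0.03, two-sided (SAP 9.1). Stop at p > 0.05 (SAP 16.5, 16.6). Planned arms of 110 and 55 (SAP 3.3).

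**Assumed, because the documents are silent.** The test statistic z at delta = 0, the fraction f of an arm with missing values (2%, 5% or 10%), and a residual SD of 1, so that deltas are in SD units.

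**Alpha split.** 0.02 + 0.03 = 0.05. The split uses the full level, and neither endpoint is itself tested at 0.05.

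**Critical values.** Two-sided |z| is 1.960 at 0.05, 2.170 at 0.03 and 2.326 at 0.02. The gaps are 2.326 − 1.960 = 0.366 for androstenedione and 2.170 − 1.960 = 0.210 for the responder.

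**Direction.** Provided p rises as delta becomes less favourable, it cannot pass 0.05 before it passes 0.02 or 0.03. Both crossings can fall on the same grid step, hence *at or beyond*.

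**Androstenedione, linear case.** If z falls linearly with delta, the overstatement of the distance to tipping is (z − 1.960)/(z − 2.326) − 1:

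| z at delta = 0 | Calculation | Overstatement |
|---|---|---|
| 3 | 1.040/0.674 − 1 | 54% |
| 4 | 2.040/1.674 − 1 | 22% |
| 5 | 3.040/2.674 − 1 | 14% |
| 6 | 4.040/3.674 − 1 | 10% |

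**Androstenedione, variance growing with delta.** Shifting a fraction f of an arm by d gives that arm variance 1 + f(1 − f)d². With SE₀ = √(1/110 + 1/55) = 0.165 and pooled variance s²(d), z(d) = (z·SE₀ − shift)/√(s²(d)·(1/110 + 1/55)). The shift is f·d if only the crinecerfont arm moves, and 2f·d if both arms move against crinecerfont. Solving for z(d) = 2.326 and z(d) = 1.960 over the three values of f, with one or both arms shifted, gives these overstatements:

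- z = 3: 46–53%
- z = 4: 22–23%
- z = 5: 14–18%

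Example with z = 4, f = 0.05 and only the crinecerfont arm shifted: at d = 3.87 the numerator is 0.661 − 0.194 = 0.467, the pooled variance is 1.474, and z(d) is about 2.33. At d = 4.74 the numerator is 0.424, the pooled variance is 1.711, and z(d) is about 1.96. The claim at 0.02 is lost at 3.9 SD, but the SAP rule reports 4.7 SD.

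**Check with multiple imputation.** Simulated regression imputation with Rubin's rules (20 imputations, 60 trials, crinecerfont arm shifted) gave median overstatements of 21.7% (5% missing) and 21.5% (10% missing) at z about 4, and 16.7% and 15.6% at z about 5.

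**Endpoint already failed at delta = 0.** For p = 0.04, z = 2.054. With 5% missing in the crinecerfont arm, the linear formula gives a reported tipping delta of (2.054 − 1.960) × 0.165/0.05 = 0.31 SD, although the claim at 0.02 was never made.

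**Responder.** Its statistic moves in steps as shifted doses cross 11 mg/m²/day, so no general percentage is given. As an illustration, assume 45/110 against 10/55 responders in an unstratified pooled test and switch crinecerfont responders to non-responders one at a time. After 7 switches p = 0.029, after 8 it is 0.038, after 9 it is 0.0495 and after 10 it is 0.064. The claim at 0.03 is lost at 8 switches; the SAP rule stops at 10.

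**The case against.** The strongest reply is that 0.05 is a deliberate nominal cut-off. Section 9.1 says "All other p-values will not be adjusted for multiplicity and should be considered as nominal p-values", Section 9.3.3 labels the sensitivity p-values nominal, Section 6.1 gives 0.05 as the general level, and the appendices spell out what they mean by not significant. The rule can be operated as written. But the nominal label says only that these p-values carry no confirmatory weight. It does not say which result is being stressed. Section 9.3.3 describes the search as finding where a statistically significant result stops being so, and for these two endpoints that is judged at 0.02 and 0.03.

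A second reply is that the same sentence governs HOMA-IR, weight and percent fat mass, where the mismatch can be larger: the first Holm step is 0.05/3 = 0.0167, or 0.01 or 0.0067 if the family level is 0.03 or 0.02. That is correct. The difference is that the Holm level for each of those endpoints depends on the other results, so no single cut-off is right and an explanatory sentence is the practical answer. The levels 0.02 and 0.03 are fixed in advance and can simply be used.

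Three points limit the size and stand:

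- Section 9.3.3 confines deltas to plausible penalties. If both crossings lie outside that range, either rule reports no tipping. In the variance model at z = 4 with 2% missing in the crinecerfont arm, they lie at 7.6 and 9.3 SD. The rule matters most with a modest z and appreciable missingness: at z = 3 with 10% missing and both arms shifted, they are 0.53 and 0.81 SD.
- The closing notes of 16.5 and 16.6 allow some deltas to be left out when significance is lost slowly, which suggests that intermediate deltas may otherwise be tabulated. A reader might then find the right crossing, but nothing requires it to be shown.
- Both crossings can coincide on the grid.

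**Conclusion.** The concern holds. For Week 4 androstenedione and the physiologic-dose responder, the stopping level in the tipping-point appendices does not match the level at which the claim is made, and the reported tipping delta is at or beyond the one where the claim is lost. This assumes that p rises as delta becomes less favourable; imputation noise could cause small local reversals.

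The illustrative overstatement for androstenedione runs from about 10% at z = 6 to about half at z = 3. The actual size is unknown. The consequence is confined to overstated robustness in one sensitivity report for two endpoints. The confirmatory tests and type I error are untouched, and Section 9.4.1 also provides a second check ("A complete-case sensitivity analysis will also be performed to test the robustness of the multiple imputation procedure"), with the same provision in 9.4.2. The change should be made, because these are the first two endpoints after the primary and the error can run in only one direction.

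**What to change.** In 16.5 step 3, set the stopping level to p > 0.02 for serum androstenedione. In 16.6 step 4, set it to p > 0.03. The p > 0.05 crossing may also be reported if labelled nominal. If either endpoint fails its own level at delta = 0, any remaining search to 0.05 should carry that label too.

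For HOMA-IR, weight and percent total fat mass, add one sentence to 16.5: 0.05 is a nominal cut-off that matches the Holm claim only when the family level is 0.05 and the other two endpoints are rejected. No Holm re-check at each delta is needed.

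The cost is two cut-offs and one sentence, with no new data or models. The reported tipping deltas for the two endpoints stay the same or become smaller.

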**Table 11: Delta-Adjustment Values**

Key Secondary Endpoint	Second Delta		If still significant after the second delta, increase or decrease delta by the following:	
	Crinecerfont	Placebo	Crinecerfont	Placebo
Serum Androstenedione (nmol/L)	0.1745	-0.1745	0.1745	-0.1745

HOMA-IR	0.1	-0.1	0.2	-0.2
Weight (kg)	1	-1	1	-1
%Total Fat Mass	1	-1	1	-1

Note that if the increment or decrement of delta is too large or too small, then the delta may be adjusted in order to make the number of comparisons reasonable. If significance is not lost or is lost slowly, some values of delta may be omitted from the final table. The tipping point will be defined as the combination of delta values that result in loss of significance.

## 16.6. Implementation of Tipping Point Analysis for the Key Secondary Endpoint: Physiologic Glucocorticoid Daily Dose Responder

This section will discuss the tipping point analysis for physiologic glucocorticoid daily dose responders which is also a key secondary endpoint as described in Section 9.4.2. This key secondary endpoint is defined as the achievement of a reduction in glucocorticoid daily dose to physiologic levels ( $\leq 11 \text{ mg/m}^2/\text{day}$  hydrocortisone equivalent adjusted for BSA) at Week 24, while Week 24 androstenedione is adequately controlled at  $\leq 120\%$  of baseline or  $\leq \text{ULN}$  for age and sex.

A tipping point sensitivity analysis will be performed to assess the robustness of the missing data assumptions for the glucocorticoid daily dose at Week 24. The following steps will be taken to implement the tipping point analysis for this key secondary endpoint:

- 1) For the 100 imputed datasets created (as described in Section 16.1), if a subject was originally missing the Week 24 value (i.e., missing the glucocorticoid daily dose at Week 24), add *delta* (see rules below) to the imputed Week 24 value. Calculate the change from baseline to Week 24 for all subjects as applicable:
  - If the Week 24 endpoint value is non-missing: change from baseline = (Week 24 value – baseline value).
  - If the Week 24 endpoint value is missing and the subject is in either the crinecerfont treatment group or placebo treatment group: change from baseline = (Week 24 delta-adjusted imputed value – baseline value).
- 2) If the subject does not have androstenedione control at Week 24 (as defined in the primary endpoint) then the change from baseline will be set to 0 prior to the analysis of the delta-adjusted imputed datasets.
- 3) Determine if each subject is a responder or a non-responder. Analyze the categorical data at Week 24 for the values in each of the 100 imputed datasets using the Cochran-Mantel-Haenszel (CMH) test. The CMH test will compare treatment groups (crinecerfont 100 mg bid vs. placebo) and will include the stratification factors used in the randomization. Use PROC MIANALYZE to combine the results and obtain the p-value.
- 4) If the p-value in the previous step was not significant (i.e.,  $>0.05$ ), then no additional analyses are needed. If the p-value was significant, repeat the previous steps using the

next values of *delta*. Continue to do this until significance is lost, or all combinations of *deltas* (defined for each treatment group) have been analyzed.

The following rules will be used for defining *delta*:

- The initial delta will be = 0 for each key secondary endpoint (ie, an analysis of the original, multiply imputed datasets)
- For subjects in the crinecerfont treatment group, the second delta will be = 1. If this is significant, continue to increase delta by 1 until significance is lost.
- For subjects in the placebo treatment group, the second delta will be = -1. If this is significant, continue to decrease delta by 1 until significance is lost.

Note that if the increment or decrement of delta is too large or too small, then the delta may be adjusted in order to make the number of comparisons reasonable. If significance is not lost or is lost slowly, some values of delta may be omitted from the final table. The tipping point will be defined as the combination of delta values that result in loss of significance.
